Comparison of the Analgesic Efficacy of a Single Shot Interscalene Block With Liposomal Bupivacaine to Bupivacaine With Dexamethasone as an adjuvant-a Randomized Controlled Trial

[name]

NCT03969875

Document Date: 6-25-2021

 Mount Sinai	Protocol Title:	COMPARISON OF THE ANALGESIC EFFICACY OF A SINGLE SHOT INTERSCALENE BLOCK WITH LIPOSOMAL BUPIVACAINE TO BUPIVACAINE WITH DEXAMETHASONE AS AN ADJUVANT-A RANDOMIZED CONTROLLED TRIAL
	Principal Investigator Name/Contact Info:	[name] MD. [name] [name]. [name] MD, PHD [name] MD [contact]
	Primary Contact Name/Contact Info	[name] MD. [contact]
	Date Revised:	
	Study Number:	

Brief Summary of Research (250-400 words):

Pain management after shoulder surgeries pose a unique challenge to the surgeon as well as the anesthesiologist. Regional anesthesia in the form of interscalene approach to the brachial plexus as an adjunct to general anesthesia or as a sole primary technique comes to one's rescue. Interscalene block either as single shot or as a catheter is an established modality for effective analgesia which facilitates early mobilization helping in physical therapy and early discharge.

With the help of local anesthetic injected as a single shot, analgesia usually lasts less than 24 hours. Though catheter with a slow infusion of local anesthesia improves quality of peri-operative pain management, it adds days to hospital stay and accompanying challenges of risk of catheter migration and additional resources for post operative follow up.

Recent research in regional anesthesia is advancing towards adjuvants which will prolong the duration of local anesthesia. This has introduced the concept of "multimodal perineural analgesia (MMPNA)" whereby multiple agents with differing mechanisms of action are used with the goal of providing perineural analgesia while avoiding exposure to high and potentially toxic levels of individual agents. Some of the commonly used adjuvants in clinical studies are fentanyl, buprenorphine, morphine, tramadol, magnesium, epinephrine, ketamine, non-steroidal anti-inflammatory drug (NSAID), midazolam, parecoxib, ketorolac, clonidine, dexmedetomidine, dexamethasone, neostigmine and potassium. They find a distinct place in wide spread clinical practice as an off label use.

Steroids have a long history of safe use in epidural space for treatment of radicular pain due to nerve irritation. Dexamethasone is used routinely as a

 Mount Sinai	Protocol Title:	COMPARISON OF THE ANALGESIC EFFICACY OF A SINGLE SHOT INTERSCALENE BLOCK WITH LIPOSOMAL BUPIVACAINE TO BUPIVACAINE WITH DEXAMETHASONE AS AN ADJUVANT-A RANDOMIZED CONTROLLED TRIAL
	Principal Investigator Name/Contact Info:	[name] MD. [name] [name]. [name] MD, PHD [name] MD [contact]
	Primary Contact Name/Contact Info	[name] MD. [contact]
	Date Revised:	
	Study Number:	

part of anti- emetic prophylaxis and anti inflammatory effect. Methyl prednisone was the first steroid to be used as an adjuvant. Dexamethasone was first used as an adjuvant in 2003.

It has been hypothesized that steroids induce a degree of vasoconstriction, thereby reducing local anesthetic absorption, tend to have an opioid sparing effect. Another theory suggests that it increases the activity of inhibitory potassium channels on nociceptive C-fibers (via glucocorticoid receptors), thus decreasing their activity.

Several studies have demonstrated promising results with the use of 8mg of perineural dexamethasone. No neuronal injury has been reported in in vivo studies. Though there are several studies which report usage of dexamethasone in varying doses of 2mg to 8mg, the optimal effective dose of dexamethasone as an adjuvant for nerve block remains unknown. Some studies have suggested perineural is more effective than IV as an adjuvant. Hence we propose to study the lowest effective dose of dexamethasone as an adjuvant which can be used as an adjuvant to local anesthesia in interscalene block for shoulder surgeries.

Liposomal bupivacaine, a formulation where bupivacaine is encapsulated into multivesicular liposomes, making it a slow and controlled release from the liposomes, was originally indicated for wound infiltration at the surgical site to provide post surgical analgesia. Studies have demonstrated efficacy upto 24 hours in femoral nerve block in total knee arthroplasty. Recent approval of liposomal bupivacaine in interscalene block for shoulder surgeries by FDA opens an arena unexplored in the world of regional anesthesia.

 Mount Sinai	Protocol Title:	COMPARISON OF THE ANALGESIC EFFICACY OF A SINGLE SHOT INTERSCALENE BLOCK WITH LIPOSOMAL BUPIVACAINE TO BUPIVACAINE WITH DEXAMETHASONE AS AN ADJUVANT-A RANDOMIZED CONTROLLED TRIAL
	Principal Investigator Name/Contact Info:	[name] MD. [name] [name]. [name] MD, PHD [name] MD [contact]
	Primary Contact Name/Contact Info	[name] MD. [contact]
	Date Revised:	
	Study Number:	

Based on the above two options in the current opioid epidemic crisis, we propose to study the analgesic efficacy of liposomal bupivacaine to bupivacaine with dexamethasone as an adjuvant in interscalene block for shoulder surgeries. Till date, there is not study comparing the two.

1) Objectives:

Research Question:

Is the analgesic efficacy of liposomal bupivacaine superior to that of bupivacaine with dexamethasone as an adjuvant in interscalene block?

Primary Outcome: The primary outcomes is the time of analgesia duration (defined as the onset of sensory discomfort that required medication) and time of motor recovery (defined as the recovery of full motor function of both wrist and elbow on the nerve block side). Time to first analgesic request, NRS at 6 hours, 12 hours, 24 hours and 48 hours, POD 3, 4, 5, 6, 7 and total narcotic consumption.

Secondary Outcome: arm weakness (0 to 24 hours, 24 to 48 hours), arm numbness (0 to 24 hours, 24 to 48 hours), nausea, vomiting, dizziness, Horner's syndrome, hoarseness, dyspnea, Intra operative narcotic consumption, PACU and hospital length of stay, pain scores as assessed by PT on POD 1, and 2.

 Mount Sinai	Protocol Title:	COMPARISON OF THE ANALGESIC EFFICACY OF A SINGLE SHOT INTERSCALENE BLOCK WITH LIPOSOMAL BUPIVACAINE TO BUPIVACAINE WITH DEXAMETHASONE AS AN ADJUVANT-A RANDOMIZED CONTROLLED TRIAL
	Principal Investigator Name/Contact Info:	[name] MD. [name] [name]. [name] MD, PHD [name] MD [contact]
	Primary Contact Name/Contact Info	[name] MD. [contact]
	Date Revised:	
	Study Number:	

patient's satisfaction scores(Yes- I would prefer the same analgesic technique the next time or No-I would prefer a different analgesic technique) and quality of sleep (good, moderate/average, bad) on POD 0 and 1. Patient reported outcomes measurement information system (PROMIS) baseline global assessment will be conducted prior to surgery and post operative pain assessment at first follow up visit. Each patient will be assessed by standardized assessment of shoulder function as recommended by American association of shoulder and elbow surgery.

2) Background

See above. There have been several studies demonstrating efficacy of dexamethasone in prolonging the analgesic effect when administered both perineurally and intra-venously as an adjuvant to local anesthesia demonstrating a dose effect relationship.

But to date there are no studies regarding the lowest effective optimal dosing as an adjuvant which can aid in analgesia and also facilitate earlier discharge from hospital avoiding nerve catheter. If an effective optimal dosing of dexamethasone as an adjuvant is deciphered, it will help in avoiding costs associated with liposomal bupivacaine facilitating earlier discharge and extending post operative analgesia avoiding narcotics.

3) Setting of the Human Research

Prospective triple blinded randomized control trial in patients undergoing elective arthroscopic shoulder surgeries. The research study will take place at Mount Sinai West hospital. The site PI is [name] MD.

 Mount Sinai	Protocol Title:	COMPARISON OF THE ANALGESIC EFFICACY OF A SINGLE SHOT INTERSCALENE BLOCK WITH LIPOSOMAL BUPIVACAINE TO BUPIVACAINE WITH DEXAMETHASONE AS AN ADJUVANT-A RANDOMIZED CONTROLLED TRIAL
	Principal Investigator Name/Contact Info:	[name] MD. [name] [name]. [name] MD, PHD [name] MD [contact]
	Primary Contact Name/Contact Info	[name] MD. [contact]
	Date Revised:	
	Study Number:	

4) Resources Available to Conduct the Human Research

For n=100, the feasibility of recruitment is manageable. Recruitment will be done through a coordination of the operating schedule and the surgeon's office.

The staff members on this protocol are all employees of Mount Sinai and will either be a resident or attending physicians that are included on the IRB protocol. There are four primary members of the research personnel:

a) [name] – Roles for [name] in this study include serving as primary investigator responsible for study design and planning, data collection, subject recruitment, manuscript writing and preparation, data analysis, safety monitoring, and responding to adverse events and/or complications. She is certified in PPHS/IRB protocols, all Citi/IRB required training in human subject protection, and has prior clinical research experience. She is also a board certified anesthesiologist and professor and chair of anesthesiology with the Icahn School of Medicine and the Mount Sinai Health System.

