Once the primary team discharges the patient, a telephone follow - up every day until resolution of any residual arm weakness/numbness will be done by the anesthesia resident originally involved in the surgery.

Patients will also be asked to note the time to first analgesic request in addition to onset of sensory discomfort and motor recovery.

a) Recruitment Methods

See above. With the HIPAA waiver requested, the surgeon will provide investigators (both of whom are physicians within the department of Anesthesiology) with information of eligible patients. After the operating room schedule has been reviewed for potential participants in the study the contact information will be obtained through the surgeon's office. Subjects will be called by the department of Anesthesiology when their surgery is scheduled, and they will be informed about the study then.

 Mount Sinai	Protocol Title:	COMPARISON OF THE ANALGESIC EFFICACY OF A SINGLE SHOT INTERSCALENE BLOCK WITH LIPOSOMAL BUPIVACAINE TO BUPIVACAINE WITH DEXAMETHASONE AS AN ADJUVANT-A RANDOMIZED CONTROLLED TRIAL
	Principal Investigator Name/Contact Info:	[name] MD. [name] [name]. [name] MD, PHD [name] MD [contact]
	Primary Contact Name/Contact Info	[name] MD. [contact]
	Date Revised:	
	Study Number:	

b) Inclusion and Exclusion Criteria

Inclusion criteria: All patients between age 18-75 years undergoing primary shoulder arthroscopic procedure. All patients who speak read and understand English will be included for follow up purposes.

Exclusion criteria included patients with patient refusal, ASA 5, presence of coagulopathy, severe lung disease, contralateral diaphragmatic palsy, insulin-dependent diabetes, hepatic disease/failure, kidney disease/failure, pregnancy, chronic opioid use (defined as opioid use for >3 months), or allergy to any of the study medications.

c) Number of Subjects

N= 100, recruit ability is manageable. Based on previous study conducted by Tandoc et al with estimated average duration of analgesia at 22 hours with dexamethasone in 0.5% bupivacaine and assumed average SD of 3 hours, they estimated that 16 patients would be needed to provide 80% power to conclude absence of effect at the significance level of 0.05 among treatment groups. To allow for 20% patient dropouts, 30 subjects per group will be targeted for enrollment.

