Data will be expressed as mean \pm SD or median with interquartile range as appropriate. Categorical data will be analyzed with Fisher exact test and chi-square test. The duration of analgesia and motor block will be analyzed by the Kaplan-Meier survival analysis and Cox

 Mount Sinai	Protocol Title:	COMPARISON OF THE ANALGESIC EFFICACY OF A SINGLE SHOT INTERSCALENE BLOCK WITH LIPOSOMAL BUPIVACAINE TO BUPIVACAINE WITH DEXAMETHASONE AS AN ADJUVANT-A RANDOMIZED CONTROLLED TRIAL
	Principal Investigator Name/Contact Info:	[name] MD. [name] [name]. [name] MD, PHD [name] MD [contact]
	Primary Contact Name/Contact Info	[name] MD. [contact]
	Date Revised:	
	Study Number:	

proportional hazards modeling. Subgroup pairwise analyses will be conducted via Kruskal-Wallis rank test with Bonferroni correction for significance. All analysis will be conducted with intent-to-treat approach to minimize the potential effects of dropout. Statistical significance will be defined as $P<0.05$.

d) Study Timelines

2018-2019 and subsequent data analysis. The subject's participation will be from time of enrollment to complete resolution of arm weakness and motor strength. Estimated date of enrollment completion will be when 100 eligible subjects are enrolled in final data analysis. Estimate date for study completion will be June 2019.

e) Study Endpoints

Primary end point will be the time of first analgesic request for the first 24 hours post operatively.

Secondary end points will be NRS at 6 hours, 12 hours, 18 hours, 24 hours, 36 hours and 48 hours and oxycodone use.

f) Procedures Involved in the Human Research

Prospective randomized controlled trial and data analysis only.
Ultrasound guided interscalene block with nerve catheter placement.

 Mount Sinai	Protocol Title:	COMPARISON OF THE ANALGESIC EFFICACY OF A SINGLE SHOT INTERSCALENE BLOCK WITH LIPOSOMAL BUPIVACAINE TO BUPIVACAINE WITH DEXAMETHASONE AS AN ADJUVANT-A RANDOMIZED CONTROLLED TRIAL
	Principal Investigator Name/Contact Info:	[name] MD. [name] [name]. [name] MD, PHD [name] MD [contact]
	Primary Contact Name/Contact Info	[name] MD. [contact]
	Date Revised:	
	Study Number:	

g) Specimen Banking

N/A

h) Data Management and Confidentiality

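### Sections 1 and 5e name different primary endpoints, neither is said to govern, and no success rule or alpha control covers them, so the primary result could be chosen after the data are seen

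*Combined protocol and SAP*

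**What the plan says.** Section 1 (Objectives, Primary Outcome) opens in the plural: "The primary outcomes is the time of analgesia duration (defined as the onset of sensory discomfort that required medication) and time of motor recovery". A sentence fragment under the same heading then adds time to first analgesic request and "NRS at 6 hours, 12 hours, 24 hours and 48 hours, POD 3, 4, 5, 6, 7 and total narcotic consumption".

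Section 5e (Study Endpoints) names one primary: "Primary end point will be the time of first analgesic request for the first 24 hours post operatively". It continues: "Secondary end points will be NRS at 6 hours, 12 hours, 18 hours, 24 hours, 36 hours and 48 hours and oxycodone use". Motor recovery does not appear in Section 5e.

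Section 5c (Number of Subjects) names no primary. Its sizing variable is analgesia duration, taken from an earlier study: "estimated average duration of analgesia at 22 hours with dexamethasone in 0.5% bupivacaine and assumed average SD of 3 hours". Its analysis text says "The duration of analgesia and motor block will be analyzed by the Kaplan-Meier survival analysis and Cox", and the sentence goes on to name the proportional hazards model. Significance is set at P<0.05 without qualification. The one multiplicity provision reads "Subgroup pairwise analyses will be conducted via Kruskal-Wallis rank test with Bonferroni correction for significance".

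The design text of Section 5 treats the time variables as separate recordings: "Patients will also be asked to note the time to first analgesic request in addition to onset of sensory discomfort and motor recovery". The data list in Section 5h includes time to first narcotic but neither onset of discomfort nor motor recovery.

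**The concern.** Two sections of the current text answer the same question differently, and nothing ranks one above the other. Motor recovery is primary in Section 1 and absent from Section 5e. Pain scores and opioid use sit under the primary heading in one place and are secondary in the other. First analgesic request is the sole primary in Section 5e, limited to 24 hours. In Section 1 it is one item in a list, with no limit.

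No decision rule is written either. The plan does not say whether the trial succeeds if any one primary outcome is significant or only if all are. Two analysts following the document could report different primary results and each cite the protocol correctly. The text does not show that such selection happened or was intended, but it permits it. A 5% false-positive rate for the primary claim is therefore not assured.

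**Working it through.** **1. The passages side by side**

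| Measure | Section 1 | Section 5e | Sizing (5c) | Kaplan-Meier/Cox (5c) |
|---|---|---|---|---|
| Analgesia duration | primary | not listed | yes | yes |
| Motor recovery | primary | not listed | no | yes (as motor block) |
| First analgesic request | under the primary heading, no time limit | sole primary, first 24 h | no | not named |
| Pain scores (NRS) | under the primary heading, 9 times | secondary, 6 times | no | no |
| Opioid use | under the primary heading | secondary (oxycodone) | no | no |

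The sizing and time-to-event text fit Section 1's first sentence. No test is expressly assigned to the Section 5e primary.

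**2. Inputs for the error rate**

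- From the documents: significance at P<0.05, with no split or hierarchy across the primary measures.
- Assumed, because the documents give neither: two-sided tests, and equal correlation ρ between the test statistics, from 0.3 to 0.9.
- Number of measures k:
  - k = 2: Section 1's two named outcomes.
  - k = 3: those two plus the Section 5e endpoint.
  - k = 13: everything under Section 1's primary heading, tested separately. That is duration 1 + motor recovery 1 + first request 1 + NRS at 6, 12, 24 and 48 h 4 + NRS on days 3 to 7 5 + narcotic consumption 1.

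**3. The plan's own level.** Any single primary fixed in advance has a 5% false-positive rate, as the P<0.05 rule intends.

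**4. If any one significant measure suffices (assumed rule)**

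Under independence, P(at least one) = 1 − 0.95^k:
- k = 2: 1 − 0.9025 = 0.0975
- k = 3: 1 − 0.8574 = 0.1426
- k = 13: 1 − 0.5133 = 0.4867

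With equal correlation ρ and c = 1.96, P(at least one) = 1 − ∫ [Φ((c − √ρ·u)/√(1−ρ)) − Φ((−c − √ρ·u)/√(1−ρ))]^k φ(u) du, integrated numerically:

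| k | ρ = 0.3 | 0.5 | 0.7 | 0.9 |
|---|---|---|---|---|
| 2 | 0.0951 | 0.0907 | 0.0835 | 0.0704 |
| 3 | 0.1362 | 0.1254 | 0.1092 | 0.0836 |
| 13 | 0.4182 | 0.3340 | 0.2407 | 0.1379 |

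If duration and first request nearly coincide (correlation 0.9) and motor recovery correlates 0.3 with each, the k = 3 figure is 0.1138.

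**5. If both Section 1 outcomes must be significant**

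P(both) = 0.05 + 0.05 − P(at least one). When neither outcome truly differs, this is 0.10 − 0.0951 = 0.0049 at ρ = 0.3 and 0.10 − 0.0704 = 0.0296 at ρ = 0.9. When one outcome truly differs, it is at most 0.05.

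**6. Whether the 24-hour limit matters**

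Take Section 5c's mean of 22 h and SD of 3 h, and assume normal times. Then P(T > 24) = 1 − Φ((24 − 22)/3) = 1 − Φ(0.667) ≈ 0.25. About a quarter of comparator patients would be censored at 24 h under Section 5e but still followed to their event under Section 1. The two wordings therefore give different analyses even if the event is the same.

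**The case against.** The strongest reply is that the document leans towards one answer. The research question concerns analgesic efficacy, and both the sizing and the survival analysis use duration of analgesia, so duration looks like the intended primary. That is a fair inference, but no sentence states it and Section 5e contradicts it.

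It can also be said that duration and first request are one event, since Section 1 ties duration to discomfort needing medication. They may well overlap. If they were identical, the three outcomes would reduce to two and the range would be 7.0–9.5%. But Section 1 lists both, the Section 5 design text records both, and the conflicts over motor recovery and the 24-hour limit would remain.

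The rule that any one outcome suffices appears nowhere, and Section 1 joins its two outcomes in a way equally compatible with requiring both. This stands: the inflation figures are conditional on that rule. The gap is that neither rule is written.

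The count of 13 needs the fragment in Section 1 to declare primaries and every pain-score time to be tested separately. Section 5e's classification suggests the fragment may be a misplaced list. This is the least secure reading, and the case does not need it.

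Finally, the Section 5h list also omits several secondary outcomes, so its silence on onset of discomfort and motor recovery may only show an incomplete list. That too is fair; it is a supporting observation.

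**Conclusion.** The point holds and must be fixed. The current text contradicts itself on the primary endpoint, and no success rule or alpha control closes the gap. The Bonferroni sentence reaches only subgroup pairwise comparisons.

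The size depends on how the gap is filled. A single prespecified primary gives 5%. Requiring both Section 1 outcomes gives 0.5–3.0% when neither truly differs and at most 5% when one does. Accepting any one gives 7.0–9.5% for two outcomes and 8.4–13.6% for three, with 11.4% for the case in which duration and first request nearly coincide. The widest reading gives 13.8–41.8%. All the correlations, and the any-one rule, are assumptions. The contradiction itself rests on the wording alone, so confidence in it is high.

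**What to change.** Name one primary endpoint and word it identically in Sections 1, 5c and 5e. Give it one definition including time zero, one observation window (saying whether the 24-hour limit is kept), and one named test at two-sided 0.05, either log-rank or Cox from the methods already planned. Match the sample-size statement to it and add the variable to the Section 5h list.

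Duration of analgesia as defined in Section 1 fits the existing sizing and survival text with least change. If first analgesic request is kept instead, realign Section 5c, assign it a test, and state in Section 5h whether time to first narcotic is the same variable.

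Make motor recovery, pain scores and narcotic consumption secondary, either Holm-adjusted or labelled supportive; which of these is a matter of preference.

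Record with a date when the choice was made and whether any unblinded data had been seen. The document is dated June 2021 and Section 5d gives a 2018–2019 timeline, so the documents do not show whether a blinded choice is still possible. If unblinded data had been seen, say so when reporting.

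The cost is text in Sections 1, 5c, 5e and 5h plus the dated record. Data collection does not change if the chosen variable is already recorded. Choosing duration requires no change in sample size on this account; keeping a 24-hour limit would mean revisiting the basis of the sizing. The loss is that motor recovery, pain scores and narcotic consumption can no longer be claimed as primary results.

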	Principal Investigator Name/Contact Info:	[name] MD. [name] [name]. [name] MD, PHD [name] MD [contact]
	Primary Contact Name/Contact Info	[name] MD. [contact]
	Date Revised:	
	Study Number:	

patients will be randomized using computer generated tables and sealed envelopes. A designated resident not involved in the study will open the sealed envelope and randomize the patient into the following groups:

Group A—Liposomal bupivacaine(133mg bupivacaine diluted normal saline total 25cc)

Group B---Dexamethasone 4mg in 0.5% Bupivacaine 25cc

The patients will be transferred to the OR to proceed with the surgery. Standard ASA monitors will be placed again and after pre oxygenation, general anesthesia will be induced with propofol and fentanyl. Laryngeal mask airway of appropriate size will be inserted and patient will be connected to the ventilator for the procedure. Maintenance of anesthesia will be achieved with sevoflurane and oxygen/air mixture. Once the procedure is completed, patients will be extubated and transferred to the recovery room(PACU) for post anesthetic care.

The patient will also receive 4mg of ondansetron intra-venous in the OR as prophylaxis for post operative nausea and vomiting.

Patients, attending anesthesiologists, surgeon and research assistant collecting the data will be blinded of the group assignment. The medication solution will be prepared by the resident physician.

 Mount Sinai	Protocol Title:	COMPARISON OF THE ANALGESIC EFFICACY OF A SINGLE SHOT INTERSCALENE BLOCK WITH LIPOSOMAL BUPIVACAINE TO BUPIVACAINE WITH DEXAMETHASONE AS AN ADJUVANT-A RANDOMIZED CONTROLLED TRIAL
	Principal Investigator Name/Contact Info:	[name] MD. [name] [name]. [name] MD, PHD [name] MD [contact]
	Primary Contact Name/Contact Info	[name] MD. [contact]
	Date Revised:	
	Study Number:	

Pain scores in the form of NRS (NUMERICAL RATING SCALE) will be assessed on arrival to PACU. Pain scores will also be assessed 1 hour after arrival to PACU and at the time of discharge from PACU. NRS scores will be assessed on the floors every 6 hourly during the first 24 hours, 8 hourly and then every 12 hourly during the second 24 hours. If NRS scores are more than 5 at any time a one-time dose of oxycodone 10mg and Tylenol 1000 mg will be given.

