Data collected in excel file to be de-identified after initial collection. Excel file be subsequently encrypted and shared only between the two above listed investigators via secure Mt. Sinai (chpnet) electronic mail.

The information included in the data will be medical record number, age, gender, ASA class, type of surgery, pain score assessments, duration of surgery, anesthesia time, time to first narcotic, total narcotic use and pain scores up to 48 hours after surgery. In case of known history of type 1 or 2 diabetes, preoperative and post operative finger stick will be recorded. Time of administration of study drug, smoking status and patient satisfaction scores will also be recorded. Only the research personnel will have access to the data. The data will be stored as a hard copy files and on a secure spreadsheet. The research personnel are responsible for the receipt of the data. The PI will keep the hard copies secure and any electronic data will be encrypted. No personal identifiers will be used. The data will undergo statistical analysis.

i) Provisions to Monitor the Data to Ensure the Safety of subjects

 Mount Sinai	Protocol Title:	COMPARISON OF THE ANALGESIC EFFICACY OF A SINGLE SHOT INTERSCALENE BLOCK WITH LIPOSOMAL BUPIVACAINE TO BUPIVACAINE WITH DEXAMETHASONE AS AN ADJUVANT-A RANDOMIZED CONTROLLED TRIAL
	Principal Investigator Name/Contact Info:	[name] MD. [name] [name]. [name] MD, PHD [name] MD [contact]
	Primary Contact Name/Contact Info	[name] MD. [contact]
	Date Revised:	
	Study Number:	

Part I: Elements of Data and Safety Monitoring Plan

MSSM Principal Monitor:

Last Name: [name]

First Name: [name]

Academic Title: Attending Physician, Professor

Department: Anesthesiology

Mailing Address: Mount Sinai West [name]

[contact]

Fax:

E-mail: [contact]

MSSM Principal Monitor:

Last Name: [name]

First Name: [name]

Academic Title: Attending Physician, Assistant Professor

Department: Anesthesiology

Mailing Address: Mount Sinai West [name]

[contact]

Fax:

E-mail: [contact]

Last Name: [name]

First Name: [name]

Academic Title: Attending Physician, Professor

Department: Orthopedics

Mailing Address: Mount Sinai West [name]

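### Patients with up to 3 months of preoperative opioid use can enrol, but their use is neither recorded nor adjusted for in the narcotic-consumption comparison

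*Combined protocol and SAP*

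**What the plan says.** **Outcome.** Section 1 (Objectives) closes the primary outcome paragraph with "POD 3, 4, 5, 6, 7 and total narcotic consumption". It gives no start, end, drug list or unit for the narcotic total. The secondary outcomes in the same section separately include "Intra operative narcotic consumption, PACU and hospital length of stay". Section 5e (Study Endpoints) instead puts the opioid measure among the secondary end points: "Secondary end points will be NRS at 6 hours, 12 hours, 18 hours, 24 hours, 36 hours and 48 hours and oxycodone use".

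**Opioid given under the protocol.** Section 5 states that "general anesthesia will be induced with propofol and fentanyl", with no dose. For a pain score above 5, "a one-time dose of oxycodone 10mg and Tylenol 1000 mg will be given".

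**Who can enrol.** The opioid exclusion in section 5b is "chronic opioid use (defined as opioid use for >3 months". Shorter use is not excluded.

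**What is recorded and analysed.** The opioid items in section 5h are "time to first narcotic, total narcotic use and pain scores up to 48 hours after surgery". Preoperative opioid use is not listed. The analysis text in section 5c names no baseline covariate for any opioid comparison.

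**The concern.** A consumption outcome is meant to show whether one block spares postoperative opioid relative to the other. A patient who arrives already taking opioid, and continues it, adds doses that reflect prior use and not how long the block lasted. Those doses vary between patients, from zero in most to possibly substantial in a few, so they add variance without treatment signal.

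Two consequences follow. A real difference is harder to detect. In addition, in a trial of this size a handful of users can split unevenly between the arms, and the listed data give the analyst no means of seeing or correcting that. Yet applying the exclusion already requires asking each patient about opioid use, so the information is obtained at screening and then not listed for recording.

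**Working it through.** **Figures in the plan.** There is none to reproduce on this point. The sample-size text in section 5c concerns duration of analgesia only (22 hours, SD 3 hours, 80% power). No SD, effect size or power is given for opioid consumption, and no prevalence or dose of preoperative use. What follows is therefore illustration under assumptions.

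**Inputs.**
- From section 5c: significance level 0.05, taken as two-sided because sidedness is not stated; total N = 100, so 50 per arm. Section 5c also mentions 30 per group. Because the comparison is set at 80% power before home opioid is added, the power figures are the same at either size; only the detectable effect changes (0.56 SD at 50 per arm, 0.72 SD at 30).
- Assumed: an 80%-power comparison on block-related opioid alone; a share p of preoperative users; their home-opioid amount, independent of arm.

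**Formula.** Let r² be the home-opioid variance divided by the block-related variance. Then power = Φ(2.802/√(1 + r²) − 1.96), where 2.802 = 1.96 + 0.842.

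**Mild case.** The user mean equals one block-related SD, and the SD among users is half that. Then r² = 0.25p + p(1 − p).

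| p | r² | Power, unadjusted |
|---|---|---|
| 2% | 0.005 + 0.0196 = 0.0246 | 79% |
| 5% | 0.0125 + 0.0475 = 0.060 | 78% |
| 10% | 0.025 + 0.09 = 0.115 | 76% |
| 20% | 0.05 + 0.16 = 0.210 | 72% |

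**Heavier case.** Block-related SD is 15 mg oxycodone-equivalent, and each user takes 40 mg over 48 h. The difference giving 80% power is 2.802 × 15 × √(2/50) = 8.4 mg. Total variance is 15² + p(1 − p) × 40².

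| p | Variance | SD (mg) | Power, unadjusted |
|---|---|---|---|
| 5% | 225 + 76 = 301 | 17.3 | 68% |
| 10% | 225 + 144 = 369 | 19.2 | 59% |
| 20% | 225 + 256 = 481 | 21.9 | 48% |

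At 20 mg instead of 40 mg, 2%, 5% and 10% users give 79%, 77% and 74%. The result is thus driven by the assumed dose and prevalence.

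**What adjustment recovers.** A none/any covariate removes the between-group term p(1 − p). In the mild case r² falls to 0.25p, that is 0.005 to 0.05, and power returns to about 78–80%. In the heavier case, where every user takes the same amount, it returns to about 80%. The one degree of freedom spent is ignored.

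**Chance imbalance.** If 10 of 100 patients are users, a split of 7–3 or worse has probability about 32%. At 40 mg each, a 7–3 split moves the arm difference by (7 − 3) × 40/50 = 3.2 mg, against the assumed 8.4 mg effect.

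**The case against.** **Randomisation already protects the comparison.** This is correct as to bias: home opioid is balanced between arms in expectation, and chance imbalance is covered by the type I error rate. It does not answer the loss of precision, which adjustment addresses.

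**The loss may be small.** This also stands. The prevalence and dose of preoperative use are not in the documents, and with few users or low doses the loss is one or two percentage points. The normal-theory figures may also overstate it for skewed data: in a simulated rank-test comparison with gamma-distributed consumption (means 14 and 24 mg), 10% users at 40 mg lowered power from 64% to 51%. That is 13 points, against 21 in the heavier case above.

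**The end point may mean rescue oxycodone only.** Section 5e can be read that way, but it does not say so, and the section 1 total carries no such limit.

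**A stronger reading is tempting.** A reader might infer that the total counts induction fentanyl and that the opioid comparison is therefore diluted. The documents do not support this. Section 1 lists intraoperative narcotic as its own outcome, section 5e names oxycodone, and the 48-hour phrase in section 5h can be read as a postoperative window. A constant dose given to everyone would not change the absolute difference or its power. The block also precedes induction, so opioid given later in surgery could respond to it. What remains on fentanyl is a missing definition.

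**The data might be recovered later.** A reader might also infer that preoperative use could never be retrieved. That goes too far: section 5h lists the medical record number and section 5 describes a thorough preoperative evaluation, so chart review may be possible, although de-identification after collection could limit it.

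**Conclusion.** The point holds as an inexpensive gain in precision. Patients with opioid use of 3 months or less are eligible, their regular opioid can enter postoperative consumption, and the plan neither lists preoperative use for recording nor adjusts for it. The comparison is not biased in expectation.

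The size cannot be derived from the documents. If the comparison had 80% power without home opioid, power would be about 72–79% with 2–20% users under the mild assumptions, and 48–68% with 5–20% users taking 40 mg over 48 h. Both ranges rest on assumed prevalence and dose; the second also assumes a block-related SD of 15 mg. The differing labels in sections 1, 5e and 5h are a secondary matter of definition.

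**What to change.** 1. At enrolment, record preoperative opioid use (none/any, and usual daily dose) from the same question used to apply the exclusion, and add it to the section 5h data list. Leave eligibility unchanged.
2. In the analysis text of section 5c, state that the consumption comparison will be adjusted for preoperative opioid use.
3. As a secondary clarification, reconcile sections 1, 5e and 5h so that the opioid outcome is postoperative opioid from PACU arrival to a fixed time, in one opioid-equivalent unit, with intraoperative narcotic reported only as its own secondary outcome. The label (primary or secondary) should agree as well.

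The cost is one data column, a covariate-adjusted model alongside the planned tests, a few sentences of text and a conversion table. With item 3, intraoperative differences no longer appear in the headline total, but they remain visible in their own outcome.
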